### Section 13: Study Design

#### Aim and Objectives

**Primary Objective:** To study the efficacy of convalescent plasma in severe COVID 19 patients in time to clinical improvement (Clinical improvement: Reduction of two points in ordinal scale or live discharge from the intensive care unit, whichever is earlier)

The six-point scale is as follows:

1. *death=6;*
2. *hospital admission for extracorporeal membrane oxygenation or mechanical ventilation=5;*
3. *hospital admission for non-invasive ventilation or high-flow oxygen therapy=4;*
4. *hospital admission for oxygen therapy (but not requiring high-flow or non-invasive ventilation)=3;*
5. *hospital admission but not requiring oxygen therapy=2;*
6. *discharged or having reached discharge criteria (defined as clinical recovery—ie, normalization of pyrexia, respiratory rate 94% on room air, and relief of cough, all maintained for at least 72 h)=1.*

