#### Secondary Objectives:

1. The proportion of patients in each category according to the ordinal scale at 48 hours and day 7, 14, and 28 after randomization
2. Duration of oxygen therapy
3. Duration of hospital stay
4. The proportion of patients on mechanical ventilation at day 7.(after randomization)

[name] [name], MD  
Additional Professor - Transfusion Medicine  
Institute of Liver and Biliary Sciences  
[name]  
[name]

5. Mortality at day 7 and day 28 (after randomization)
6. Duration of Intensive Care Unit stay
7. Incidence of adverse effects in both groups
8. Presence of antibodies against SARS-CoV-2 in serum on days 0, 3, 7, 14, 21 & 28 after plasma administration, as long as the patient remains in the hospital.
9. Cytokines and acute phase reactants
10. To study the titers in COVID-19 convalescent plasma donors and correlate with duration of illness, the severity of symptoms, duration of hospital stay, drugs used in therapy, duration between recovery, and donation.

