**Study Design:**

An open label randomized controlled trial.

The study group will comprise of adult patients with severe COVID -19 as detailed above. Randomization will be done in the ratio of 3:1 in with 150 patients in the treatment arm and 50 patients in the control arm. Allocation concealment will be done by Sequentially Numbered Opaque Sealed Envelopes (SNOSE) method.

[name] [name], MD  
Additional Professor - Transfusion Medicine  
Institute of Liver and Biliary Sciences  
[name]  
[name]

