#### **Patient Monitoring**

All included patients will be randomized to receive either 500 ml of convalescent plasma in two doses of 250 ml on two consecutive days along with the standard of care or standard of care alone

Clinical information of all enrolled patients including symptoms at presentation, time to presentation to the hospital, and development of pulmonary symptoms will be recorded. The details of comorbid diseases as measured by the Charlson index of co-morbidity and Acute Physiology and Chronic Health Evaluation II (APACHE II). Details of cross-sectional imaging, chest-x-ray, bacterial or fungal co-infections, and details of antibiotic treatment will be recorded. Development of complications including shock, acute kidney injury, acute coronary syndrome, myocarditis, acute respiratory distress syndrome, need for mechanical ventilation and nosocomial infection will be recorded. The use of high-flow oxygen, non-invasive, and invasive ventilation will follow standard guidelines and will be recorded. The details of antiviral treatment will be recorded for all enrolled patients.

[name] [name], MD  
Additional Professor - Transfusion Medicine  
Institute of Liver and Biliary Sciences  
[name]  
[name]

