## Flow Chart

- All variables shall be expressed in mean (SD) or median (range)
- Variables will be compared by Mann- Whitney U test
- For Categorical variables, we will use Chi-Square or Fisher's test
- Survival analysis will be done using Cox-proportional regression analysis

The actuarial probability of survival shall be calculated by Kaplan- Meier graph and compared by the log-rank test.

[name] [name], MD  
Additional Professor - Transfusion Medicine  
Institute of Liver and Biliary Sciences  
[name]  
[name]

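### Day-7 and day-28 mortality would most naturally be compared by an unadjusted chi-square or Fisher test; adjusting for pre-randomisation APACHE II and Charlson scores would be a modest, optional improvement

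*Protocol*

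**What the plan says.** The primary objective is time to clinical improvement. Item 5 of the secondary objectives (Section 13) is "Mortality at day 7 and day 28 (after randomization"), so mortality is secondary. The statement of expected outcome, after the standard-of-care details, nevertheless says that the study will settle whether there is a mortality benefit.

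The statistical methods are a short generic list under the Flow Chart heading. It says "For Categorical variables, we will use Chi-Square or Fisher's test", then "Survival analysis will be done using Cox-proportional regression analysis", and closes with "The actuarial probability of survival shall be calculated by Kaplan- Meier graph and compared by the log-rank test". No line is tied to a named endpoint and no covariate is listed.

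Under Patient Monitoring (Section 14) the protocol names comorbid disease "as measured by the Charlson index of co-morbidity and Acute Physiology and Chronic Health Evaluation II (APACHE II"). The sentence has no verb and gives no time point, and the scores are given no role in the analysis.

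Under Study Design: "Randomization will be done in the ratio of 3:1 in with 150 patients in the treatment arm and 50 patients in the control arm". Sealed envelopes are named for concealment. No stratification or minimisation is stated.

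**The concern.** Death by day 7 and death by day 28 are yes/no outcomes at fixed times, so the categorical line is their natural home. A chi-square or Fisher test cannot take account of baseline severity, and the log-rank test is also written without adjustment. The Cox model could carry covariates, but none is named, and the list does not say which method governs mortality.

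With no stratification stated and 50 controls planned, the arms may differ in severity by chance. In a trial where that happens, the unadjusted risk difference mixes the severity difference with the plasma effect. It may show a difference where there is none or hide a real one. Adjusting for a prognostic score fixed before randomisation removes most of this and tightens the estimate somewhat. The trial already names two candidate scores.

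**Working it through.** **Plan's own figure.** The sample size section gives only the arm sizes, with no alpha, power, mortality rate or effect size, so nothing can be reproduced beyond 150/50 = 3, which agrees with the stated 3:1.

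**Inputs from the protocol.** 150 plasma and 50 control patients; mortality at day 7 and day 28.

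**Assumed inputs (the protocol gives none).** Two-sided 5% level; control mortality 15% to 30%; odds of death 2 to 3 times higher per SD of a severity score. The only mortality rate the protocol reports for COVID-19 plasma recipients is an external 7-day figure of 14.9% (Table 2), close to the low end of that range.

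**Step 1: size of chance imbalance.** For a baseline score scaled to SD 1, the SD of the difference in arm means is sqrt(1/150 + 1/50) = sqrt(0.00667 + 0.02000) = 0.163. Then 0.25/0.163 = 1.53, and the two-sided normal probability beyond that is 0.126, or about 13% of trials. At 100:100 the SD would be sqrt(2/100) = 0.141 and the probability 7.7%. The 3:1 split therefore raises the SD by about 15% (0.163/0.141 = 1.155).

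**Step 2: what an imbalance does to the mortality difference.** Assume a log-odds of death of 1.0 per SD. Shift the score by +0.75d in controls and -0.25d in plasma patients, with d = 0.25 SD, and average the logistic risk over a normal score. With no treatment effect, the apparent difference is about 3.6 points at 20% mortality and 4.5 points at 30%. Across the scenarios of Step 3, an imbalance of one SD of its chance distribution (0.163) moves the unadjusted difference by 1.2 to 3.1 points, against a sampling SD of that difference of 5.4 to 7.5 points.

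**Step 3: simulation at 150:50.** 8,000 trials per scenario, one normal score, uncorrected chi-square against the Wald test from a logistic model adjusted for the score.

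| Quantity | Unadjusted | Adjusted |
|---|---|---|
| Null rejection, all trials | 4.5% to 4.9% | 3.9% to 4.7% |
| Null rejection, trials with imbalance above 0.25 SD (about 12%) | 6.5% to 10.9% | 3.9% to 4.4% |
| Power, treatment odds ratio 0.4, 15% mortality, score odds ratio 2 | 44% | 42% |
| Same, score odds ratio 3 | 40% | 40% |
| Power, treatment odds ratio 0.4, 30% mortality, score odds ratio 2 | 61% | 62% |
| Same, score odds ratio 3 | 54% | 59% |

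Simulation error is about 0.5 points for overall null rejection, 1.1 points for power, and up to 2 points in the imbalanced subset.

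**Step 4: the remedy itself.** A further simulation with two covariates and a standardised risk difference gave an SD 1% to 9% smaller than the unadjusted difference in every scenario. In trials with imbalance above 0.25 SD, null rejection fell from 7-11% to 4-7%. Power changed by about -4 to +4 points.

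**Step 5: a more favourable setting.** With 4,000 trials per scenario and the likelihood-ratio test, power for 30% against 15% mortality rose from 63% to 67%, 63% to 70% and 64% to 72% as the score became more prognostic. For 20% against 8% the gain was about 0 to 5 points. Under the null at 20% mortality that test rejected in 5.3% to 5.8% of trials.

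**The case against.** The strongest reply is that nothing here is wrong. Randomisation makes the unadjusted test valid, because chance imbalance is part of its sampling error. Step 3 bears this out: the overall level stays at or just below 5%. A reader might infer that the planned test is biased or that its false-positive rate is inflated. The protocol and the figures do not support that. The raised rejection rate belongs to the subset of unlucky trials and is already averaged into the overall level.

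A reader might also infer that the protocol confines mortality to an unadjusted test. It does not. The line after the categorical one names a Cox model, which can carry covariates, and mortality is not expressly assigned to any line. Choosing covariates can properly be left to a statistical analysis plan, so the absence of a covariate list is not itself a fault. What remains is narrower: the one method named that fits fixed-day binary mortality excludes covariates, so an adjusted analysis of it would need a change to that line.

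Three further points stand. The Patient Monitoring sentence does not establish that the scores are taken before randomisation; in an open-label trial, adjusting for a later value could introduce bias. The power benefit is not dependable, and at 15% mortality, close to the only rate the protocol reports, there is none. The 3:1 split matters little, since most of the imbalance would also be present at 100:100.

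**Conclusion.** The point holds as an optional improvement to a secondary endpoint. The categorical line would compare mortality without using severity information that the trial already names. In the roughly 13% of trials with an imbalance of at least 0.25 SD, the estimate can move by a few percentage points; adjustment removes most of that and reduces the SD of the risk difference by 1% to 9%. The case rests on protection against an unlucky draw and on a small gain in precision. It should not be argued on power, where the simulations range from about -4 to +8 points.

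The imbalance figures follow from the arm sizes alone. Everything about deaths rests on assumed mortality and assumed prognostic strength, since the protocol gives neither for its own patients.

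**What to change.** In the statistical methods, state that the main comparison of day-7 and day-28 mortality is a logistic model with arm, APACHE II and Charlson index, using values recorded at or before randomisation, reported as a standardised risk difference with 95% CI. Enter the same two covariates in the Cox model for survival. Keep the chi-square or Fisher result as a sensitivity analysis. In Patient Monitoring, complete the sentence on the two scores and give their time point.

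The cost is mainly wording, provided that pre-randomisation values are in fact collected; if they are not, a data-collection rule is needed as well. A few missing scores will need simple imputation. The likelihood-ratio test can be slightly liberal when deaths are few (5.3% to 5.8% in Step 5). The change should be made before outcome data are examined, because the trial is open label and adjustment added later would invite doubt.

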**Study Population:**

Adult patients with severe COVID -19 infections defined as WHO Interim Guidance and the Guideline of Diagnosis and Treatment of COVID-19 of National Health Commission of China (version 5.0) with confirmation by real-time RT-PCR assay with severe disease i.e. meeting any 2 of the following criteria

1. Patients on ventilator (in last 24 hours)
2. Respiratory distress, RR  $\geq$ 30 beats/min
3. Oxygen saturation level less than 93% in resting state
4. Partial pressure of oxygen (PaO2)/oxygen concentration (FiO2)  $\leq$  300 mmHg
5. Lung infiltrates > 50% within 24 to 48 hours

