### Section 14: Inclusion and exclusion criteria for the admission of patients in the study

#### Inclusion criteria

Patients with severe COVID-19 (as described above) will be considered for randomization and will be transfused Convalescent Plasma within 3 days of symptom onset (Severe COVID-19)

**Severe COVID -19 defined** by WHO Interim Guidance and the Guideline of Diagnosis and Treatment of COVID-19 of National Health Commission of China (version 5.0) along with confirmation by real-time RT-PCR assay with severe disease i.e. meeting any 2 of the following criteria-

- Patients on ventilator (in last 24 hours)
- Respiratory distress, RR  $\geq$ 30 beats/min
- Oxygen saturation level less than 93% in resting state

[name] [name], MD  
Additional Professor - Transfusion Medicine  
Institute of Liver and Biliary Sciences  
[name]  
[name]

- Partial pressure of oxygen (PaO2)/oxygen concentration (FiO2) ≤ 300 mmHg
- Lung infiltrates > 50% within 24 to 48 hours

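### The primary endpoint depends on the baseline ordinal score, but neither randomisation nor analysis names it as a stratum; stratifying by it is a nearly free gain in efficiency

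*Protocol*

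**What the plan says.** The primary objective (Protocol, Aim and Objectives) is time to clinical improvement, defined as "Reduction of two points in ordinal scale or live discharge from the intensive care unit, whichever is earlier". The six-point scale includes "hospital admission for extracorporeal membrane oxygenation or mechanical ventilation=5" and "hospital admission for oxygen therapy (but not requiring high-flow or non-invasive ventilation)=3". Score 4 is non-invasive ventilation or high-flow oxygen, score 2 is in hospital without oxygen, and score 1 is discharge or discharge criteria held for 72 hours.

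Patients qualify by "meeting any 2 of the following criteria" (Study Population). "Patients on ventilator (in last 24 hours" is one of the five, so patients both on and off a ventilator can enter.

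On allocation, Study Design says: "Randomization will be done in the ratio of 3:1 in with 150 patients in the treatment arm and 50 patients in the control arm". Sealed envelopes conceal the sequence, and no stratification factor is named. Two hospitals are listed under Treatment Centres.

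The statistical methods under Flow Chart list Mann-Whitney, chi-square or Fisher tests, a Cox regression, and survival probabilities "calculated by Kaplan- Meier graph and compared by the log-rank test". They assign no test to time to clinical improvement and name no stratum or covariate. Baseline severity is recorded in any case: Patient Monitoring lists the Charlson index and APACHE II, and the baseline ordinal score is needed to derive the endpoint.

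**The concern.** A two-point fall is a different task for each patient. From score 5 it means coming off mechanical ventilation or ECMO to low-flow oxygen. From 4 it means needing no oxygen at all. From 3 it means discharge or sustained discharge criteria. The starting score is therefore part of the event definition and is likely to predict how soon the event occurs.

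Two things follow if it is left out of the comparison. First, with a control arm of 50, the arms can differ noticeably in starting severity by chance, and an open-label result is then harder to interpret unless the adjustment was fixed in advance. Second, pooling patients with unlike event rates in one log-rank test pulls the apparent hazard ratio toward 1 and costs power when the effect is constant within score groups.

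**Working it through.** **What can be reproduced.** The plan's only figure is the enrolment aim, 150 + 50 = 200. No alpha, power, effect size or event rate is given, so it cannot be re-derived. A two-sided 5% level and a 28-day horizon (the last ordinal-scale time point among the secondary objectives) are assumed below.

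**Step 1: chance imbalance.** Assume 30% are ventilated at baseline; the documents give no mix.

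- SD of the difference in proportions = √[0.3 × 0.7 × (1/150 + 1/50)] = √(0.21 × 0.02667) = 0.0748.
- 95% range = ±1.96 × 0.0748 = ±0.147, or ±14.7 percentage points.
- A gap above 10 points in either direction: 0.10/0.0748 = 1.34 SD, which occurs in about 18% of trials.

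**Step 2: is precision scarce?** Schoenfeld's formula for 80% power at 3:1 is events = (1.960 + 0.842)² / [0.75 × 0.25 × (ln HR)²].

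| True HR | Events for 80% power | Power with 150 events |
|---|---|---|
| 1.3 | 609 | 29% |
| 1.5 | 255 | 58% |
| 1.75 | 134 | 84% |
| 2.0 | 88 | 96% |

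At a hazard ratio of 1.5, more events are needed than there are patients, so a gain in efficiency is worth having.

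**Step 3: what stratifying buys.** Trials of 150 against 50 were simulated, 1,500 per cell, with exponential times recorded in days and censored at day 28. The hazard ratio was constant within strata. Scores 3/4/5 were mixed 40/40/20%, or 10/80/10% in the last scenario. Control 28-day event rates are given in the order 3/4/5. The second hospital's hazard was multiplied by 1.2 in the moderate and last scenarios, by 1.3 in the strong one, and by 1 otherwise. All of these inputs are assumptions, including which score does better.

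| Scenario (control rates) | HR | Unstratified | By score | By score and centre |
|---|---|---|---|---|
| Not prognostic (60/60/60%) | 1.5 | 52% | 53% | 52% |
| | 1.75 | 80% | 79% | 79% |
| Mild (75/65/50%) | 1.5 | 53% | 55% | 54% |
| | 1.75 | 80% | 82% | 81% |
| Moderate (85/65/35%) | 1.5 | 46% | 56% | 54% |
| | 1.75 | 72% | 83% | 81% |
| Strong (95/65/20%) | 1.5 | 30% | 53% | 54% |
| | 1.75 | 53% | 82% | 83% |
| Moderate rates, 80% at one score | 1.5 | 50% | 54% | 54% |
| | 1.75 | 79% | 83% | 82% |

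With a true hazard ratio of 1, rejection was 4 to 6% for every test. Stratifying by score never cost more than about 1 point of power. Stratifying by centre alone changed power by less than 2 points in every scenario. The Monte Carlo standard error near 50% is √(0.25/1500) = 1.3 points, so differences of about a point in the table should not be read as real.

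**The case against.** A reader might infer that the protocol commits the primary endpoint to an unstratified log-rank test and so ignores baseline severity. The text does not say that. The log-rank sentence has survival as its subject, and mortality is a secondary objective. The Cox regression listed just before it could carry the baseline score. Strata and covariates are often left to a statistical analysis plan, and none is shown here. Silence is not a decision, and this objection stands. What remains is that the two time-to-event methods written down name no stratum, while the need for one follows from the protocol's own endpoint definition.

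A reader might also infer that baseline score must dominate the endpoint. Different target states do not show how far event rates differ, and the documents give neither rates nor a baseline mix. Leaving intensive care alive counts at any score, and the exclusion of patients with multi-organ failure, on vasopressors or moribund may narrow the spread further. This also stands, and it is why the gain is given as a range starting at nil.

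Third, no invalidity is shown. Chance imbalance under randomisation is already reflected in the test's error rate, and type I error was near 5% with or without strata. The smaller pooled hazard ratio is a marginal quantity, where the stratified one is conditional on score. The issue is one of efficiency and of which effect is estimated.

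Finally, nothing here shows a material benefit from stratifying by centre, and no gain was demonstrated for further covariates such as age or APACHE II.

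**Conclusion.** The point holds as a recommended improvement. The endpoint sets a different target at each baseline score, a mix of scores can enter, and neither the randomisation nor the listed methods name that score. Prespecifying it as a stratum is better than the methods as written.

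The size of the benefit is uncertain. Under the assumed rates it runs from about nil (score not or only mildly prognostic), through about 10 points of power (moderate), to 23 to 29 points (strong). It is about 3 to 5 points if 80% of patients share one score. The imbalance figure of ±14.7 points depends on the assumed 30% ventilated. The conclusion that stratifying costs almost nothing held in every scenario examined. The documents do not support calling the planned test biased or invalid.

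**What to change.** Add to the statistical methods, before outcomes are reviewed, that time to clinical improvement is compared by a log-rank test stratified by baseline ordinal score. The hazard ratio and its confidence interval should come from a Cox model stratified the same way, so that test and estimate correspond, and the unstratified result should be reported as supportive. State that the stratified hazard ratio is conditional on baseline score, and how a sparse score group would be merged. A patient entering at score 2 could meet the endpoint only by leaving intensive care alive, so say how any such patient is placed. Centre may be added as a stratum if wished, but not in the expectation of more power.

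The cost is a few sentences. No new data, patients or visits are needed, because the baseline score must be recorded to derive the endpoint.

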**Section 15: Work Plan with the schedule of activities giving milestones**

An RCT which will be completed within 4 months

**Section 16: Permission from Drug Controller of India for use of drug/vaccine/device in the study, wherever applicable-**

ILBS Blood Centre has a license for Plasmapheresis and approval of DCGI

**Section 17: Safety of the proposed interventions, drugs, or vaccine to be tested including results of relevant laboratory and animal toxicity and safety trials, and results of studies carried out in humans**

Human studies have been done and reported rare SAEs\*, it has been approved by CDC under emergency Investigational New Drug Applications (eINDs)

**Section 18: Description of plans to withdraw or withhold standard therapy in the course of research-No****Section 19: For research carrying more than minimal risk, an account of plans to provide medical therapy for such risk or injury –Insurance cover for patients**

**The donor may have any of the adverse events related to Plasmapheresis donation (similar to healthy apheresis donors) – Detailed in Donor Information Sheet**

